6.0 Data and Specimen Banking

Biomarker specimens will be collected and stored at the study sites (University of Minnesota - Tobacco Research Programs, [name] and Hormel Institute – [name]) until delivery to the Masonic Cancer Center's [name] laboratory for storage and analysis. Samples that are not used for the primary analysis of study biomarkers will be banked for future use. The banked samples will be stored until analyses and destroyed if it is determined they are no longer needed. The samples, which may also include DNA or RNA, may be stored up to a maximum of 10 years from the study's end. A subject has the right to withdraw consent at any time by informing the Principal Investigator by following the instructions provided in the consent

PROTOCOL TITLE: Watercress in Detoxification of Environmental Toxicants and Carcinogens

VERSION DATE: July 23, 2020

and HIPAA documents. If this occurs, any remaining identifiable research sample(s) will be destroyed.

Data will be stored in a secure database (RedCap) at the study site at the University of Minnesota, Masonic Cancer Center. Only study personnel directly involved with the study will have access to the linked records. The samples that will be transferred to the laboratory or stored for future analyses will be de-identified. We will not be transferring data that has any identifying information over the Internet.

Biomarker samples (blood, urine, saliva and buccal/oral cells) that are banked after the completion of the primary analyses will be stored at the Masonic Cancer Center [name] laboratory located at the Cancer and Cardiovascular Research Building for future use.

No identifying information will be shared with outside investigators. If used in any collaborative efforts beyond the scope of this study, any shared data will be de-identified. However, records for the study may be reviewed by departments at the University with appropriate regulatory oversight. The records may also be reviewed by a representative of the funding agency, National Institutes of Health, and the Food and Drug Administration.

7.0 Sharing of Results with Participants

Information will not be shared with participants.

8.0 Study Population

Inclusion Criteria:

1. Male or female age 18 years or older. Participants can be smokers or non-smokers;
 - a. Smokers must report daily use (at least one cigarette per day)
2. In good physical health with no unstable or serious medical conditions as determined by the licensed medical professional;
3. In stable and good mental health (i.e. not currently, within the past 6 months, experiencing unstable or untreated psychiatric diagnosis, including substance abuse) as determined by the licensed medical professional;
4. Not using any medications that may affect the Nrf2 pathway;
5. Women who are not pregnant or nursing or planning to become pregnant;
6. Participants have provided written informed consent to participate in the study.

Exclusion Criteria:

1. Significant immune system disorders, respiratory diseases, kidney or liver diseases or any other medical disorders that may affect biomarker data as determined by the licensed medical professional;
2. History of Type I or II diabetes;
3. Vital signs outside of the following range (participants failing for vital signs will be allowed to re-screen once):

PROTOCOL TITLE: Watercress in Detoxification of Environmental Toxicants and Carcinogens

VERSION DATE: July 23, 2020

- a. Systolic BP < 90 or \geq 160 mmHg
- b. Diastolic BP < 50 or \geq 100 mmHg
- c. Heart rate < 45 or \geq 105 bpm
- 4. Not willing to abstain from eating cruciferous vegetables during the course of the study;
- 5. Known allergy or contraindication to watercress or any of the study product components;
- 6. PKU disease (as some of the flavoring packets contain phenylalanine).

Participants who agree to go through the telephone screening process will be assigned a screening number and taken through a screening questionnaire. Participants who meet the eligibility criteria described above will be invited to participate in a virtual screening visit, where the entire study will be explained in detail, informed consent will be obtained and the screening measures will be completed.

9.0 Vulnerable Populations

No vulnerable populations will be used.

10.0 Local Number of Participants

Three hundred and fifty participants are needed for the study. Anticipating a 15% attrition rate, a total of 400 of participants will be enrolled into the study. We expect about 300 non-smokers and about 100 smokers.

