3.0 Study Endpoints/Events/Outcomes

The primary endpoint is to conduct a clinical trial with 350 subjects (both non-smokers and smokers) to determine the effects of the watercress preparation on detoxification of environmental toxicants and carcinogens.

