Measurements: For the comparison between the two treatment groups, we will consider measurements excluding the baseline observation. Measurements will be taken from each subject in the two supplementation sequences as seen in the following diagram:

Group 1: Period #1 (watercress; A1) – washout – Period #2 (placebo; B2)

Group 2: Period #1 (placebo; B1) – washout – Period #2 (watercress A2)

The letter is used to denote supplementation (A for watercress and B for placebo) and the number, 1 or 2, denotes the period. We will assume, in the formulation of statistical models, that the measurements A1, A2, B1, and B2 are “normally distributed” in log-scale. These letters can represent one of our outcome variables: urinary mercapturic acid levels of specific toxicants (e.g. benzene, acrolein, crotonaldehyde, propylene oxide, etc.) or for mercapturic acids generally, or DNA adducts of acrolein.

Main Outcome Variables: Our data analysis will be based on the following “outcome variables”:

$$X1 = B2 - A1; \text{ and } X2 = B1 - A2.$$

This subtraction will cancel the “within-sequence” effects of all subject-specific factors, leaving only two to be modeled and analyzed: the Treatment (or Supplementation) effect and the Period (or Order) effect. The measurements will result in two independent samples. Each will have the same sample size if there are no dropouts or missing data. Otherwise the number of subjects for each group of measurements (i.e., X1 and X2) will differ if there are dropouts and missing data.

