We would obtain values of X1 or X2, which is a log of "ratio" for each subject in each of the two groups with different supplementation order, it's (watercress/placebo) for group 1 and (placebo/watercress) for group 2. We'll then compute the averages of these log ratios, i.e \bar{x}_1 and \bar{x}_2 . We will do this calculation separately for the double null group ($\hat{\alpha}_{nn}$), and single null group ($\hat{\alpha}_{np}$). We will compare this average ratio with the average ratio of the double positive group ($\hat{\alpha}_{pp}$). With the double nulls being about 15% of the population, *GSTM1* single nulls (45%) and *GSTT1* single nulls (23%), we expect to see 60 double nulls, 180 *GSTM1* single nulls, 92 *GSTT1* single nulls, and 68 double positive individuals. If there is no influence of *GSTM1* or *GSTT1*, the effect of watercress supplementation would be the same between the double null and the double positive group or between the single null and the double positive group. We will test for the significance of the genotypic effect by using a two-sample t test.

PROTOCOL TITLE: Watercress in Detoxification of Environmental Toxicants and

Carcinogens

VERSION DATE: July 23, 2020

In order to estimate the power for that comparison, we need information on the variability of mercapturic acid levels within and between subjects. We will compute the variances of each of these genotypic groups separately and then obtain a pooled variance estimate to compute our pooled t test statistic. Based on our previous work, we used an intra-subject CV of 0.4 and an inter-subject CV of 0.6, which translates to a pooled standard deviation of 0.657. According to Table 3, the percentage difference between the Placebo and PEITC groups with the double null genotypes varied from 29.8% to 95.4%, whereas the percentage difference for the double positive genotypes varied from 4% to 7%. In general, we will have 80% power to detect a difference of 35% between the double null and double positive group and given the range of difference between these two groups in Table 3, we expect to have good power to study this interaction between watercress and *GSTM1* or *GSTT1* genotypes.

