22.0 Multi-Site Research

PROTOCOL TITLE: Watercress in Detoxification of Environmental Toxicants and Carcinogens

VERSION DATE: July 23, 2020

A total of 400 of participants will be enrolled into the study. Each site will recruit smokers and non-smokers using various media sources (flyers, newspaper ads, Craigslist, Facebook, etc.).

Regular teleconferences will be scheduled between the two sites to discuss the study procedures, recruitment, and any safety concerns.

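### At the plan's own 15% attrition, 400 enrolled leaves 340, not the 350 stated as needed, and the genotype counts in section 15.0 are for all 400 enrolled

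*Combined protocol and SAP*

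**What the plan says.** Section 10.0 (Local Number of Participants) sets the requirement: "Three hundred and fifty participants are needed for the study". The next sentence gives the allowance for loss: "Anticipating a 15% attrition rate, a total of 400 of participants will be enrolled into the study". Section 3.0 repeats the smaller figure ("The primary endpoint is to conduct a clinical trial with 350 subjects (both non-smokers and smokers") and section 22.0 the larger one ("A total of 400 of participants will be enrolled into the study"). No section reconciles the two.

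Section 15.0 applies shares of 15%, 45% and 23%, with the remainder double positive, to obtain its genotype counts. It begins "we expect to see 60 double nulls" and goes on to 180 GSTM1 single nulls, 92 GSTT1 single nulls and 68 double positives. It also expects about 100 smokers as 25% of the sample.

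The planned contrasts in section 15.0 are X1 = B2 - A1 and X2 = B1 - A2, each a within-person difference between the two periods. On the measurements that enter them it says "we will consider measurements excluding the baseline observation". It recognises that losses matter: "Otherwise the number of subjects for each group of measurements (i.e., X1 and X2) will differ if there are dropouts and missing data". It gives no counts after losses.

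The power statement is: "In general, we will have 80% power to detect a difference of 35% between the double null and double positive group". It names no group sizes, alpha, sidedness or effect scale.

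**The concern.** The attrition allowance should turn the number needed into the number to enrol. Here the three figures given together (350, 15%, 400) do not fit: at the stated rate, the stated enrolment does not leave the stated need.

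Section 15.0 adds a second inconsistency. Its counts describe the enrolled sample, while the t-test it plans runs on people with usable data in both periods. A colleague who checks the power claim with 60 double nulls and 68 double positives would be using groups that the plan itself expects to shrink. At stake is whether the reader can tell which sample size the trial is designed around and which one supports the power claim.

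**Working it through.** **Enrolment arithmetic.** Inputs from section 10.0: need 350, attrition 15%, enrol 400.

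- Expected to remain: 400 x (1 - 0.15) = 340.
- Shortfall: 350 - 340 = 10, and 10/350 = 2.9%.
- Enrolment needed for 350 at 15%: 350/0.85 = 411.8, so 412.
- Attrition at which 400 leaves 350: 1 - 350/400 = 12.5%.
- A possible source of 400: 350 x 1.15 = 402.5, rounded. This is an inference; the plan does not show its calculation.

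**Base of the genotype counts.** Shares from section 15.0: 15%, 45%, 23%, remainder 17%.

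| Group | Share | x 400 (as printed) | x 340 |
|---|---|---|---|
| Double null | 15% | 60 | 51.0 |
| GSTM1 single null | 45% | 180 | 153.0 |
| GSTT1 single null | 23% | 92 | 78.2 |
| Double positive | 17% | 68 | 57.8 |
| Total | 100% | 400 | 340 |

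The printed counts are exactly the shares of 400. The 100 smokers at 25% imply the same base.

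**Who is lost to the t-test.** At 15% attrition, 400 - 340 = 60 people leave. This is an approximate figure and not a limit in either direction. Section 5.0 schedules visits on days 4, 7 and 14 of each period, so someone who leaves late in period 2 may still supply X1 or X2. Others who finish may drop out of the analysis: section 15.0 names missing data separately from dropouts. Section 5.0 also defers the blood draw used for genotyping until University policy allows it, with a recall visit for those already finished. Oral cells are stored for DNA isolation, so a missed draw need not mean a missing genotype.

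**Power by base.** The plan gives SD 0.657, a difference of 35% and a two-sample t-test. I assume two-sided alpha 0.05, which is not stated, and read 35% in two ways. With n1 = 0.15N and n2 = 0.17N, the standard error is 0.657 x sqrt(1/n1 + 1/n2). Power comes from the noncentral t distribution with n1 + n2 - 2 degrees of freedom and noncentrality equal to effect divided by standard error.

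| N | n1, n2 | 35% = 0.35 log units | 35% = log(1.35) = 0.300 |
|---|---|---|---|
| 400 | 60, 68 | 84.7% | 72.5% |
| 350 | 52.5, 59.5 | 79.6% | 66.7% |
| 340 | 51, 57.8 | 78.5% | 65.4% |

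The plan's 80% is reproduced most closely at N = 350 with 0.35 log units (79.6%; 80.3% by the normal approximation). From 350 to 340 the loss is about 1 point on either reading. From 400 to 340 it is about 6 to 7 points.

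**The case against.** The strongest reply is that this is rounding. The enrolment figure lies within 3% of 412, the cost is about 1 point of power, and section 10.0 does not explicitly call the 350 completers. The materiality part stands, and it is why the point is minor. The rest does not remove the inconsistency. Attrition is mentioned only to get from 350 to 400, so 350 is naturally the number meant to remain, and at the stated rate it does not.

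A second reply is that losses may turn out smaller. Section 15.0 anticipates little missing data, and section 11.0 pays a bonus of $245 for completion and compliance. Both are relevant, but neither gives a rate, and section 10.0 does give one: 15%.

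A third is that the mixed model in section 15.0 can use people with one period only. That is so, but the power statement is attached to the two-sample t-test on the contrasts.

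A reader might go further and infer that the 80% power was inflated by using the enrolled counts. The documents do not support that. The power sentence carries no group sizes, and under one plausible reading 80% matches 350 rather than 400. A reader might also take 60 as the most that could be lost to the t-test. That does not hold either, because missing samples or genotypes are additional to attrition.

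**Conclusion.** Minor, but wrong as written. The enrolment shortfall (340 against 350) and the enrolled base of the genotype counts follow from the plan's own figures and need no assumption beyond reading 350 as the number meant to remain.

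The power figures rest on more: two-sided 0.05, SD 0.657, the plan's genotype shares, and a choice of scale for 35%. Under those assumptions the 10-person shortfall matters little. The larger gap, between the printed counts and those expected after attrition, affects anyone who takes 60 and 68 as the analysed groups. It does not show that the authors' own power figure is too high, because the base of that figure is not stated. This is an inconsistency in reporting and does not threaten the design.

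**What to change.** In sections 3.0 and 10.0, do one of the following:

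1. State that 400 enrolled gives about 340 expected completers at 15% attrition, and change the sentence that gives 350 as the number needed.
2. Keep 350, state that 400 enrolled delivers it only if attrition is at most 12.5%, and give the reason for expecting that rate.

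In section 15.0, label 60, 180, 92 and 68 as enrolled. Add the expected completers, about 51, 153, 78 and 58 at 340. Restate the power at the chosen completer number with its base, alpha, sidedness and the scale of the 35% difference. Under option 1, that restatement is also what shows whether 340 is enough.

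The cost is text only. Enrolling 412 would also close the gap, but with about 1 point of power at issue this correction does not require it. The downside is a slightly less favourable stated size and power.

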11.0 Local Recruitment Methods

We will recruit smokers and non-smokers using various media sources (flyers, newspaper ads, Craigslist, Facebook, etc.). We will also recruit participants who have previously participated in other research studies through the Tobacco Research Programs and agreed to be contacted for future studies.

For each clinic visit, the participant will be paid \$25 for the screening visit. Eligible participants will be paid \$10 for transportation costs and \$25 for time spent at each visit ($12 \text{ visits} \times \$35 = \$420$). A \$245 bonus will be provided for completion and compliance to the study procedures (including biochemical validation of watercress consumption by measurement of PEITC-NAC in urine) for a total of \$690.

12.0 Withdrawal of Participants

A study participant may be discontinued from the study if investigators determine that this is the best decision in order to protect his/her safety. In the event that a participant either withdraws from the study or the investigators decide to discontinue a participant due to an adverse event (AE) or serious adverse event (SAE), the participant will have appropriate follow-up assessments and if necessary, referrals will be made for medical care. The participant experiencing an AE/SAE will be followed until the problem resolves, stabilizes, or is clearly unrelated to the study product. Any AE that remains open will be reviewed and closed at the last study visit.

PROTOCOL TITLE: Watercress in Detoxification of Environmental Toxicants and Carcinogens

VERSION DATE: July 23, 2020

For the participant's protection, they will be withdrawn immediately from the study if any of the following occur:

- 1) Cardiovascular disease (CVD) event: Typically includes MI (heart attack), PTCA (angioplasty/stenting), bypass surgery, stroke, or peripheral vascular disease. Less common CVD problems would be new cardiac arrhythmias (e.g., new atrial fibrillation) or new valvular disease (e.g., mitral or aortic regurgitation).
- 2) DVT/PE (deep vein thrombosis/pulmonary embolism, i.e., blood clots in the venous system).
- 3) Suicide Attempt: A participant will be withdrawn if he/she attempts suicide at any time during participation in the study.
- 4) Psychiatric Hospitalization: A participant will be withdrawn if he/she is hospitalized for psychiatric reasons at any time during participation in the study.
- 5) Pregnancy: If a participant becomes pregnant, she will be immediately withdrawn from the study. In addition, the licensed medical professional will follow-up after delivery to ask questions about the health of the baby.

The following will be monitored and can lead to the participant being withdrawn by the Principal Investigators or Medical Monitor:

- 1) Blood pressure (BP) or heart rate (HR) changes: If any of the following occur post-enrollment:
 - 1) BP is at or above 160 systolic/100 diastolic; 2) BP is below 90 systolic/50 diastolic and the participant is experiencing symptoms listed on the 'Blood Pressure and Heart Rate Symptom Checklist'; 3) HR is at or above 105 bpm; 4) or below 45 bpm and the participant is experiencing symptoms listed on the 'Blood Pressure and Heart Rate Symptom Checklist'.
- 2) Medication changes: If a participant begins taking any of the exclusionary medications or other medications that could potentially have an interaction post-enrollment, the licensed medical professional will determine how best to monitor and minimize potential risks (including withdrawal if warranted).
- 3) Any hospitalization or debilitation in which participation in the study could be detrimental to the recovery process. This will be self-reported by the participant and reviewed by the investigators and medical professional to determine if continued participation in the study is appropriate.
- 4) If a participant is behaving in an inappropriate or threatening manner, admits to lying about eligibility criteria, including omitting previous medical diagnoses and medications, is participating in other tobacco research studies that could affect the primary outcome measures, does not follow study instructions, etc., then he/she can be withdrawn at the investigators' discretion.

Participants will be informed about the withdrawal at the visit and data collection will stop. No additional procedures will be conducted if participants are withdrawn. We will ask that all unused product be returned along with completed dosing diaries.

PROTOCOL TITLE: Watercress in Detoxification of Environmental Toxicants and Carcinogens

VERSION DATE: July 23, 2020

13.0 Risks to Participants

The potential risks for participants recruited for this study are minimal. Physiological and subjective measures will be noninvasive and should present no psychological or medical risk to the subject. Blood and oral samples will be obtained by trained study personnel. Watercress in doses that are administered has the potential to lead to gastrointestinal distress (e.g. flatulence, bloating, nausea). Participants will be under medical supervision throughout their study participation and adverse symptoms will be recorded at each clinic visit and monitored by the project Co-PIs [name] and [name] along with the study's licensed medical professional.

Pregnant women will not be recruited. If participants choose to be sexually active, they should use an appropriate "double barrier" method of birth control (such as female use of a diaphragm, intrauterine device (IUD), or contraceptive sponge, in addition to male use of a condom) or the female should be using prescribed "birth control" pills, injections, or implants. Female participants with child-bearing potential will be tested for pregnancy at the first clinic visit using the first morning void urine sample. If a participant becomes pregnant during the study, she will be withdrawn from the study. Approximately 30 days after being withdrawn or having a positive pregnancy test, the research staff will call the participant to confirm her due date. The licensed medical professional will follow-up with the participant after delivery to ask questions about the baby's health.

14.0 Potential Benefits to Participants

While there might not be any direct benefit to the participant, if proven effective, watercress can become part of a health maintenance diet to possibly reduce risks for certain cancers by enhancing the detoxification of toxicants and carcinogens.

15.0 Statistical Considerations

Descriptive statistics will be used to summarize subject characteristics, for example subject demographics (age and gender, race, ethnicity, income, current occupation and usual occupation), medical history and current health status for current diagnoses, symptoms and past health problems. Categorical variables will be described by their frequencies and the continuous measurements will be described by their mean, median, range, and standard deviations. We will use paired *t*-test to compare distributions of continuous variables (e.g., age, number of cigarettes per day, number of pack-years of cigarettes smoked over lifetime) between the two treatment groups (watercress and placebo arms). The McNemar's Chi-squared test will be used to compare categorical variables, such as sex, *GSTM1* and *GSTT1* genotypes between the two treatment groups.

The statistical analysis section particularly focuses on Specific Aim 3, which investigates the hypothesis that detoxification of these noxious agents by conjugation with glutathione, as indicated by mercapturic acid levels in urine, will be significantly elevated compared to placebo in subjects who consumed the watercress preparation and are null for *GSTM1*, *GSTT1*, or both. We can test for a Period x Treatment interaction such as testing if the effect of the watercress preparation varies depending on whether it is given in the first period compared to the second period.

PROTOCOL TITLE: Watercress in Detoxification of Environmental Toxicants and

Carcinogens

VERSION DATE: July 23, 2020

We will have baseline measurements on each subject. Participants will be asked to attend clinic visits on days 0 (baseline), 2, 7 and 14 for each of the periods they are receiving product (watercress or placebo). We will compare the baseline measurements on the outcome variables and some important covariates between the two treatment groups through the two-sample t test to see if there is any significant difference between the two groups in order to ensure homogeneous treatment groups. We will also perform repeated data analysis using the measurements on each subject and consider different baseline parameters for the watercress and the placebo group in our multivariate regression analysis described later.

Measurements: For the comparison between the two treatment groups, we will consider measurements excluding the baseline observation. Measurements will be taken from each subject in the two supplementation sequences as seen in the following diagram:

Group 1: Period #1 (watercress; A1) – washout – Period #2 (placebo; B2)

Group 2: Period #1 (placebo; B1) – washout – Period #2 (watercress A2)

The letter is used to denote supplementation (A for watercress and B for placebo) and the number, 1 or 2, denotes the period. We will assume, in the formulation of statistical models, that the measurements A1, A2, B1, and B2 are “normally distributed” in log-scale. These letters can represent one of our outcome variables: urinary mercapturic acid levels of specific toxicants (e.g. benzene, acrolein, crotonaldehyde, propylene oxide, etc.) or for mercapturic acids generally, or DNA adducts of acrolein.

Main Outcome Variables: Our data analysis will be based on the following “outcome variables”:

$$X1 = B2 - A1; \text{ and } X2 = B1 - A2.$$

This subtraction will cancel the “within-sequence” effects of all subject-specific factors, leaving only two to be modeled and analyzed: the Treatment (or Supplementation) effect and the Period (or Order) effect. The measurements will result in two independent samples. Each will have the same sample size if there are no dropouts or missing data. Otherwise the number of subjects for each group of measurements (i.e., X1 and X2) will differ if there are dropouts and missing data.

We would obtain values of X1 or X2, which is a log of "ratio" for each subject in each of the two groups with different supplementation order, it's (watercress/placebo) for group 1 and (placebo/watercress) for group 2. We'll then compute the averages of these log ratios, i.e \bar{x}_1 and \bar{x}_2 . We will do this calculation separately for the double null group ($\hat{\alpha}_{nn}$), and single null group ($\hat{\alpha}_{np}$). We will compare this average ratio with the average ratio of the double positive group ($\hat{\alpha}_{pp}$). With the double nulls being about 15% of the population, *GSTM1* single nulls (45%) and *GSTT1* single nulls (23%), we expect to see 60 double nulls, 180 *GSTM1* single nulls, 92 *GSTT1* single nulls, and 68 double positive individuals. If there is no influence of *GSTM1* or *GSTT1*, the effect of watercress supplementation would be the same between the double null and the double positive group or between the single null and the double positive group. We will test for the significance of the genotypic effect by using a two-sample t test.

PROTOCOL TITLE: Watercress in Detoxification of Environmental Toxicants and

Carcinogens

VERSION DATE: July 23, 2020

In order to estimate the power for that comparison, we need information on the variability of mercapturic acid levels within and between subjects. We will compute the variances of each of these genotypic groups separately and then obtain a pooled variance estimate to compute our pooled t test statistic. Based on our previous work, we used an intra-subject CV of 0.4 and an inter-subject CV of 0.6, which translates to a pooled standard deviation of 0.657. According to Table 3, the percentage difference between the Placebo and PEITC groups with the double null genotypes varied from 29.8% to 95.4%, whereas the percentage difference for the double positive genotypes varied from 4% to 7%. In general, we will have 80% power to detect a difference of 35% between the double null and double positive group and given the range of difference between these two groups in Table 3, we expect to have good power to study this interaction between watercress and *GSTM1* or *GSTT1* genotypes.

We will also perform the above analysis separately for smokers and non-smokers. We expect to see about 25% smokers (~ 100 smokers) in our sample. We might have limited power to detect the impact of watercress for the double-nulls among the smokers, however this subgroup analysis would reveal if there are suggestive differences in the association of urinary mercapturic acid levels, watercress and *GSTM1*, *GSTT1* between the smokers and the non-smokers.

Multivariate Regression Analysis: We will use multivariate regression analysis to supplement the t-test by pooling the data together and using each of the primary outcome variables as dependent variable, separately. In addition to the variables representing the supplementation, treatment order, and status of *GST (M1, T1)* genotypes, the list of independent variables will include socio-demographic characteristics such as gender, age, smoker vs non-smoker, baseline smoking level (cigarettes per day), and intake of dietary nutrients. We will fit a linear mixed-effect model where the dependency in the repeated measurements on each individual will be captured through a random effect. The status of *GST (M1, T1)* genotypes will be modeled as fixed-effects and we will test for the null hypothesis of no association between the genotypes and each outcome. Our primary parameter of interest will be the interaction between the treatment order (pre vs post) and the genotype groups (double null, *GSTM1* single null, *GSTT1* single null, and double positives). We will perform a t-test to assess the significance of the interaction parameter. The residual covariance structure should be selected among several candidates, i.e. autoregressive, compound symmetry, unstructured, etc., to estimate the fixed and random effects. We do not anticipate much missing data on the participants. In general, we will assume missingness at random (MAR) and the likelihood-based linear mixed effect model will provide consistent estimates of our parameters of interest in presence of MAR. The models will be assessed through their Akaike's Information Criterion and Bayesian's Information Criterion. The normality of the outcome variables will be assessed and in presence of non-normality, we will also implement Generalized Estimating Equations to study the impact of watercress and genotypes on each outcome variable. We will use the statistical software R packages nlm and gee to perform the above analysis. These packages will also provide the flexibility to fit non-linear mixed effect models to assess the impact of watercress and genotype groups.

PROTOCOL TITLE: Watercress in Detoxification of Environmental Toxicants and Carcinogens

VERSION DATE: July 23, 2020

A variety of measures will be taken to ensure data accuracy and completeness. The regular research team meetings will include discussions of proper methods for data collection, transmission, and storage, limiting data collection to those in protocol required to answer a research question, de-identifying data, and encryption methods.

A comprehensive data dictionary will be created to specify definitions and value codes for all variables that will be entered into REDCap and other study databases. Electronic forms for the collection of subjective measures via REDCap will include programming features to ensure valid data (i.e., input masks, validation criteria, skipout logic) and will be stored on the University of Minnesota, HIPAA compliant, computing system. Double entry will be used for all other de-identified data entered into REDCap. Biological specimens will be labeled with barcode labels that incorporate the participant ID. The secured biospecimen website will identify the location of each sample at the clinic (prior to submission to the laboratory) and in the [name] laboratory.

Oversight of the randomization and product distribution will be conducted by the Project Manager in collaboration with the co-Principal Investigators. The randomization schedules and the link between the alphabetic code and treatment assignment will be maintained securely by the Project Manager. An Online Randomization and Product Tracking database will be created in collaboration with the study biostatistician. This database will be used to track product purchases, product inventory, and assignment of study product to participants based on the randomization schedule.

Quality control procedures will be conducted for all data collected, including analysis of missing data, and logic checks for out of range and other anomalous values. Queries will be made regarding such data issues, with documentation of any changes made in the data.

